14.4 Clinical relevance of these correlative studies

1. Identification of patients who are likely to have the maximum benefit from ibrutinib maintenance therapy.
2. Identification of patients who are likely to have a rapidly vs. delayed response to ibrutinib maintenance therapy.
3. Identification of patients who are likely to have a prolonged vs. a short-lived response.

4. Identification of *additional* targets within the BTK pathway that can be exploited concurrently to optimize the response from ibrutinib in eradication of MRD.
5. Identification of molecular landscape associated with CLL clone resistant to ibrutinib therapy.
6. Potential development of biomarkers of clinical response/resistance.

15.0 Drug Information

15.1 Ibrutinib (ImbruvicaTM, PCI-32765)

15.11 **Background:** Ibrutinib is an antineoplastic agent that is an inhibitor of Bruton's tyrosine kinase.

15.12 **Formulation:** Ibrutinib comes in a capsule: either size 0, gray. 140 mg capsules or size 2, yellow immediate-release 70 mg capsules. The capsules also contain the following compendial excipients: microcrystalline cellulose, croscarmellose sodium, sodium lauryl sulfate, and magnesium stearate. Capsules are packaged in high-density polyethylene bottles with an induction seal and a child resistant screw-top cap. The number of capsules in each aclar blister pack or per bottle is indicated on the label.

15.13 **Preparation and storage:** All formulations should be stored according to the storage conditions indicated on the label. Ibrutinib capsules: 70 mg and 140 mg

15.14 **Administration:** Administer orally with water at approximately the same time every day. Ibrutinib can be taken with or without food. Swallow capsules whole; do not open, break, or chew the capsules. Ibrutinib should be held at least 3-7 days pre- and post- surgery depending upon the type of surgery and the risk of bleeding. Hazardous agent; use appropriate precautions for handling and disposal.

15.15 **Pharmacokinetic information:**

- a) Absorption – Current data indicates bioavailability is low and displays high inter-subject variability. The median time to reach maximum plasma concentration (T_{max}) is approximately 2 hours. Administration of ibrutinib in a fasted condition resulted in approximately 60% of exposure as compared to administration either in fed condition (30 minutes after a high-fat breakfast), or when drug was taken 30 minutes before or 2 hours after a meal. Based on data for the effects of food, ibrutinib could be taken with or without food at approximately the same time each day.
- b) Distribution: The plasma protein binding of ibrutinib and its metabolite PCI 45227 in human plasma is 97.3% and 91%, respectively. The apparent steady state volume of distribution is approximately 10,000 L.
- c) Metabolism – Ibrutinib is extensively metabolized by CYP3A4/5 (major) and CYP2D6 (minor). The half-life elimination is 4-6 hours. Ibrutinib is metabolized in the liver.

d) Excretion –The excretion of ibrutinib is predominantly via the feces with approximately 80% recovered mostly within 2 days, whereas ~8% is excreted in urine. Approximately 1% of the ibrutinib is recovered as unchanged drug, all in feces. Overall, these PK characteristics resulted in minimal accumulation of both parent compound and metabolite PCI-45227 on repeated daily dosing of ibrutinib.

e) Special populations: a small increase in bioavailability was estimated with increasing age. Exposure is predicted to increase approximately 14% and decrease approximately 20% in subjects of 81 and 49 years of age, compared to a typical 67-year old subject. No statistically significant effects were observed for the other covariates tested, i.e., sex, race, mild and moderate renal impairment, mild hepatic impairment and B-cell histology. The recommended doses for patients with mild and moderate liver impairment are 280 mg/day and 140 mg/day (Child-Pugh Class A and B, respectively). It is not recommended to administer ibrutinib to subjects with severe hepatic impairment (Child-Pugh Class C).

15.16 **Potential Drug Interactions:** Ibrutinib is primarily metabolized by cytochrome P450 enzyme 3A4/5. Voriconazole and posaconazole can be used concomitantly with ibrutinib as per the dosing guidance described in the specific clinical study protocol. All other strong inhibitors of CYP3A (eg, ketoconazole, indinavir, nelfinavir, ritonavir, saquinavir, clarithromycin, telithromycin, itraconazole, nefazodone, and cobicistat) should be avoided, and an alternative with less CYP3A inhibitory potential should be considered. If the benefit outweighs the risk and a strong CYP3A inhibitor must be used, see the recommended dose modifications described in the specific clinical study protocol.

If a moderate CYP3A inhibitor (eg, fluconazole, erythromycin, amprenavir, aprepitant, atazanavir, ciprofloxacin, crizotinib, diltiazem, fosamprenavir, imatinib, verapamil, amiodarone, dronedarone) is indicated in patients with B-cell malignancies, reduce the ibrutinib dose to 280 mg for the duration of the inhibitor use or as per recommended dose modifications described in the specific clinical study protocol. No ibrutinib dose modifications for moderate inhibitors are required in patients with cGVHD dosed with ibrutinib 420 mg.

No dose adjustment is required in combination with mild inhibitors. Monitor patient closely for toxicity and follow dose modification guidance as needed. Avoid grapefruit and Seville oranges during ibrutinib treatment as these contain moderate inhibitors of CYP3A.

Administration of ibrutinib with strong inducers of CYP3A decreases ibrutinib plasma concentrations by up to 90%. Avoid concomitant use of strong CYP3A inducers (eg, carbamazepine, rifampin, phenytoin and St. John's Wort). Consider alternative agents with less CYP3A induction.

To minimize the potential for an interaction in the GI tract, narrow therapeutic range P-gp or BCRP substrates such as digoxin or methotrexate should be taken at least 6 hours before or after ibrutinib.

Ibrutinib may also inhibit BCRP systemically and increase the exposure of drugs that undergo BCRP-mediated hepatic efflux, such as rosuvastatin.

There have been reports of bleeding-related events in subjects treated with ibrutinib. Warfarin or other vitamin K antagonists should not be administered concomitantly with ibrutinib unless specified in the protocol. Supplements such as fish oil and vitamin E preparations should be avoided.

15.17 Known potential toxicities:

- Common(1 to <10%: febrile neutropenia, atrial fibrillation, diarrhea, pyrexia, pneumonia,
- Uncommon/Rare (<1%): leukocytosis, thrombocytopenia, 1, vision blurred, stomatitis, gastritis, asthenia, bronchitis, lung infection, sinusitis, urinary tract infection, neutrophil count decreased, platelet count decreased, dehydration, hyperuricemia, myalgia, extremity pain, dizziness, hematuria, epistaxis, erythematous rash, maculo-papular rash, hematoma, hypertension, cellulitis, infection, lower respiratory tract infection, sepsis, skin infection, arthritis, bone pain, flank pain, basil cell carcinoma, squamous cell carcinoma, syncope, acute kidney injury, pleural effusion, respiratory failure, macular rash, hypotension, respiratory tract infection, leukostasis syndrome, pancytopenia, atrial flutter, cardiac failure, myocardial infarction, colitis, intestinal obstruction, oral mucosal blistering, systemic inflammatory response syndrome, atypical pneumonia, bacteremia, infectious enterocolitis, neutropenic sepsis, periorbital cellulitis, pneumonia (pneumocystis jirovecii, bacterial, cryptococcal, fungal, haemophilus, influenzal, viral, pseudomonal klebsiella, legionella, parainfluenzae viral, streptococcal, organising), septic shock, urosepsis, post procedural hemorrhage, subdural hematoma, tumor lysis syndrome, pain (pelvic, groin), hemorrhage intracranial, lung infiltration, pneumonitis, pustular rash, breast cellulitis, bronchopulmonary aspergillosis, Escherichia sepsis, viral lower respiratory tract infection, pneumococcal sepsis, fungal sinusitis, staphylococcal infection, staphylococcal skin infection, interstitial lung disease, angioedema, hypertensive crisis, chronic sinusitis bacteroides bacteremia, orbital cellulitis, staphylococcal cellulitis, Escherichia bacteremia, alveolitis allergic, Stevens-Johnson syndrome, Haemophilus bacteremia/sepsis, pseudomonal lung infection, bacterial sepsis, herpes zoster disseminated, muscle hemorrhage, cerebral hemorrhage, deep vein thrombosis, squamous cell carcinoma of the skin, basosquamous carcinoma of the skin, hepatic failure, ventricular tachyarrhythmia
- Cardiac Arrhythmias: Atrial fibrillation, atrial flutter, and cases of ventricular tachyarrhythmia including some fatal events, have been reported in subjects treated with ibrutinib,

particularly in subjects with cardiac risk factors, hypertension, acute infections, and a previous history of cardiac arrhythmia. Periodically monitor subjects clinically for cardiac arrhythmia. Subjects who develop arrhythmic symptoms (eg, palpitations, lightheadedness, syncope, chest discomfort or new onset of dyspnea) should be evaluated clinically, and if indicated, have an ECG performed. For cardiac arrhythmias which persist, consider the risks and benefits of ibrutinib treatment, and follow the dose modification guidelines

- **Cerebrovascular accidents:** Cases of cerebrovascular accident, transient ischemic attack, and ischemic stroke including fatalities have been reported with the use of ibrutinib in the post-marketing setting, with and without concomitant atrial fibrillation and/or hypertension. Regular monitoring and appropriate treatment of conditions that can contribute to the occurrence of these events is recommended.
- Cutaneous vasculitis has been identified as a new adverse reaction in the postmarketing setting

Please refer to the prescribing information or Investigator's Brochure for a more complete comprehensive list of treatment-emergent adverse events.

15.18 **Drug procurement:** Drug will be provided free of charge to study participants by Pharmacyclics, Inc.

15.19 **Nursing Guidelines:**

- There are numerous drug to drug interactions. Record all of patient's medications including OTC, and herbal use. Avoid concomitant use with agents as listed in section 15.16.
- Patients should be instructed to avoid eating grapefruit (including juice) and Seville oranges while on ibrutinib.
- Peripheral edema is common. Instruct patients to report this to the study team.
- Gastrointestinal side effects are common (diarrhea, nausea, constipation, abdominal pain, vomiting, etc). Treat symptomatically and monitor for effectiveness of intervention.
- Monitor CBC w/diff. Instruct patients in energy conserving lifestyle (anemia) and to report any unusual bruising or bleeding and/or signs or symptoms of infection to study team.
- Arthralgias, Myalgias, and muscle spasm can be seen. Treat symptomatically and monitor for effectiveness.
- Monitor renal function/uric acid levels, especially in patients who may be experiencing dehydration.
- Respiratory symptoms may include, cough, SOB, and URI. Instruct patients to report these symptoms to the study team.
- Rarely patients can experience secondary skin cancers. Instruct patients to report any new skin lesions to the study team.
- Rash can be seen. Instruct patient to report to study team.
- Cardiac arrhythmias have been seen with this agent including a-fib, atrial flutter and ventricular tachyarrhythmia's, some of which have led to death.

Instruct patients who experience any palpitations, lightheadedness, syncope, or SOB to see medical care immediately. This is especially important in patients who have pre-existing cardiac issues.

- Warn patients of the risk of bleeding. Patients should not take warfarin or other vitamin K antagonists while on ibrutinib, unless the protocol allows for it. Additionally, patients should be cautioned to avoid fish oil and Vitamin E supplements.
- Patients who are concurrently on ibrutinib and ventoclax should be monitored closely for excess toxicity.

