7.11 Ibrutinib

- 420mg PO QD will begin on day one of cycle #1.
- Four weeks will constitute 1 treatment cycle.
- Patients will be evaluated for MRD status every 3 cycles (as discussed previously in Section 4.0, footnote 8, see detailed MRD section 11.4).
- A maximum of 36 cycles of maintenance cycles will be given.
- Treatment will be discontinued if (a) patients develop unacceptable side effects, (b) if patients develop disease progression while on ibrutinib maintenance (recommended to be confirmed on two independent occasions at least 2 week apart and consistent with the IWCLL guidelines, see Section 11.0), (c) if patients have completed the 36 cycles on maintenance therapy, (d) if the patient is removed from the study by the treating physician due to concern of overall wellbeing and in the best interest of the patient, (e) patients who have residual disease at the end of 36 cycles will continue to event monitoring

7.2 Treatment by Local Medical Doctor (LMD): If patient is tolerating therapy without excessive toxicity at a stable dose level after 1 cycle (can be confirmed through telecommunication and does not need to be physically evaluated at Mayo Clinic) of treatment the patient may be seen by their primary physician (if outside of Mayo Clinic). Results would need to be returned to Mayo Clinic. Patient would need to return to Mayo Clinic every 3 cycles for follow-up at Mayo Clinic.

7.3 After the first 6 months, clinical evaluation and blood tests can be obtained per test schedule and mailed/faxed to Mayo Clinic and patient can return at least every 3 cycles for follow up to Mayo (patient does not need to be seen every cycle). Patient may be seen more frequently, as clinically necessary. All unused study drug must be returned, and all study drug must be accounted for. A 3-month supply of study drug may be provided at each cycle.

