8.0 Dosage Modification Based on Adverse Events

8.1 Dose Levels (Based on Adverse Events in the Tables below)

| Dose Level | Ibrutinib |
|------------|--------------|
| 0* | 420 mg daily |
| -1 | 280 mg daily |
| -2 | 140 mg daily |

* Dose level 0 refers to the starting dose.

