9.2 Supportive care

Patients should receive full **supportive care**, including transfusions of blood and blood products, antibiotics, and antiemetics when appropriate. (A) **Any blood transfusions administered must be irradiated blood products to reduce risk of transfusion-mediated graft versus host disease in CLL patients receiving T-cell suppressive therapy. Leukocyte reduction of all blood products for patients on protocol is also required.** All blood products and concomitant medications such as antidiarrheals, analgesics, and/or antiemetics received from the first day of study treatment administration until 30 days after the final dose will be recorded in the medical records. (B) **Antiemetics** may be used at the discretion of the attending physician. (C) **Prophylactic antibiotics and antifungals** may be prescribed at the treating physicians' discretion and as clinically indicated, or as per the institutional guidelines. (D) Treatment for autoimmune cytopenias are permitted for <14 days at doses that do not exceed 100 mg per day of prednisone or equivalent. (E) Supportive medications in accordance with standard practice (such as for emesis, diarrhea, etc.) are permitted. (F) Short courses (≤ 14 days) of steroid treatment for non-cancer related medical reasons (e.g., joint inflammation, asthma exacerbation, rash, antiemetic use and infusion reactions) at doses that do not exceed 100mg per day of prednisone or equivalent are permitted.

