9.4 Treatment related lymphocytosis

Lymphocytosis has been reported with ibrutinib, however since this is a patient population who are already expected to be in remission post induction therapy it is not known if this lymphocytosis will still happen upon treatment with ibrutinib. Patients who develop this reaction will be monitored as per standard clinical protocol without specific intervention unless other specific symptoms / signs of disease progression is noted (such as increase in lymph node size that is progressive and persist beyond 3 months of

maintenance therapy, worsening of cytopenia from the time of initiation of maintenance therapy that is consistent with the IWCLL guidelines requiring therapeutic intervention, development of B symptoms persisting for more than 2 months while on therapy or other factors such as organomegaly demonstrating disease progression).

9.5

Medications to be used with caution

CYP3A-Inhibitors/Inducers: Ibrutinib is metabolized primarily by CYP3A. Avoid co-administration with strong CYP3A4 or moderate CYP3A inhibitors and consider alternative agents with less CYP3A inhibition.

If a strong CYP3A inhibitor (eg, ketoconazole, indinavir, nelfinavir, ritonavir, saquinavir, clarithromycin, telithromycin, itraconazole, nefazadone, or cobicistat) must be used, reduce ibrutinib dose to 140 mg or withhold treatment for the duration of inhibitor use. Subjects should be monitored for signs of ibrutinib toxicity.

If a moderate CYP3A inhibitor (eg, voriconazole, erythromycin, amprenavir, aprepitant, atazanavir, ciprofloxacin, crizotinib, darunavir/ritonavir, diltiazem, fluconazole, fosamprenavir, imatinib, verapamil, amiodarone, or dronedarone) must be used, reduce ibrutinib to 140 mg (for 840 mg/day dose, reduce to 280 mg) for the duration of the inhibitor use. Avoid grapefruit and Seville oranges during ibrutinib/placebo treatment, as these contain moderate inhibitors of CYP3A (see Section 5.3.1.2).

No dose adjustment is required in combination with mild inhibitors.

Avoid concomitant use of strong CYP3A inducers (eg, carbamazepine, rifampin, phenytoin, and St. John's Wort). Consider alternative agents with less CYP3A induction.

A comprehensive list of inhibitors, inducers, and substrates may be found at <http://medicine.iupui.edu/clinpharm/ddis/main-table/>. This website is continually revised and should be checked frequently for updates.

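### A 420 mg patient who must take a moderate CYP3A inhibitor is sent to 140 mg by section 9.5, but section 15.16 prints 280 mg and does not say that 9.5 governs

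*Combined protocol and SAP*

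**What the plan says.** The starting dose is fixed in section 7.11: "420mg PO QD will begin on day one of cycle #1". Section 8.1 gives two reduced levels, 280 mg (level -1) and 140 mg (level -2).

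Section 9.5 (medications to be used with caution) first discourages the combination: "Avoid co-administration with strong CYP3A4 or moderate CYP3A inhibitors and consider alternative agents with less CYP3A inhibition". If a moderate inhibitor has to be used, the instruction is to "reduce ibrutinib to 140 mg (for 840 mg/day dose, reduce to 280 mg) for the duration of the inhibitor use". The 280 mg figure there belongs to a starting dose of 840 mg a day, which this trial does not use.

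Section 15.16 (potential drug interactions) covers the same situation. For patients with B-cell malignancies, which include CLL, it says to lower the "dose to 280 mg for the duration of the inhibitor use or as per recommended dose modifications described in the specific clinical study protocol".

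The nursing guideline in 15.19 sends staff to the second of these sections: "Avoid concomitant use with agents as listed in section 15.16".

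**The concern.** Two sections of one protocol give different doses for the same patient on the same interacting drug. The clause at the end of the 15.16 sentence could resolve this if it clearly handed over to 9.5, but it is joined by an *or*, so 280 mg remains a printed option. It also names no section. A reader who looks for dose modifications by title reaches section 8.0, "Dosage Modification Based on Adverse Events", which contains no CYP3A rule.

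A clinician or nurse working from 15.16 alone could therefore give twice the dose that 9.5 requires. The situation is discouraged but foreseeable:

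- Exclusion 3.29b covers only strong CYP3A modulators, so needing a moderate inhibitor does not bar entry under that criterion.
- Section 9.2(C) allows "Prophylactic antibiotics and antifungals" at the treating physician's discretion, and 9.2(B) says antiemetics "may be used at the discretion of the attending physician".
- Treatment runs for up to 36 cycles, and section 7.2 lets a primary physician outside the centre see the patient after cycle 1. Such a physician is more likely to rely on the written text.

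**Working it through.** This is a comparison of texts with simple dose arithmetic; no statistical quantity is involved.

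**1. Do the two rules cover the same drugs?** Section 15.16 names 13 moderate inhibitors: fluconazole, erythromycin, amprenavir, aprepitant, atazanavir, ciprofloxacin, crizotinib, diltiazem, fosamprenavir, imatinib, verapamil, amiodarone and dronedarone. Section 9.5 names 15: these 13 plus voriconazole and darunavir/ritonavir. The overlap is 13 of 13, so the difference in dose cannot be explained by different drugs.

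**2. Do they cover the same patients?** Section 15.16 limits its 280 mg to B-cell malignancies, and every trial patient has B-CLL. Section 9.5 applies to every trial patient. The answer is yes.

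**3. How far apart are the doses, starting from 420 mg?**

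| | Section 9.5 | Section 15.16 as printed |
|---|---|---|
| Dose | 140 mg | 280 mg |
| 140 mg capsules | 1 | 2 |
| Fraction of 420 mg | 140/420 = 0.33 | 280/420 = 0.67 |
| Reduction | 1 − 0.33 = 67% | 1 − 0.67 = 33% |
| Level in 8.1 | -2 | -1 |

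The ratio is 280/140 = 2 and the difference is 280 − 140 = 140 mg a day. Section 9.5 is consistent with itself: its 840 mg rule gives 280/840 = 0.33, the same fraction as 140/420.

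**4. Can the sections be reconciled?** Test each dose against each section.

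- 140 mg meets 9.5 directly and meets 15.16 through its second alternative.
- 280 mg meets 15.16 through its first alternative and fails 9.5, which offers no 280 mg option at 420 mg.

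Only 140 mg satisfies both, but 15.16 does not tell the reader that.

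**5. Does the text lead a reader of 15.16 to 9.5?** Section 8.0 mentions CYP3A 0 times. Section 15 mentions section 9.5 0 times. The pointer in 15.19 goes to 15.16.

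**6. Could supportive care bring these drugs in?** By ordinary drug class, which is an assumption because the documents do not classify them, 4 of the 13 fall in groups that 9.2(B) or 9.2(C) permits: fluconazole (antifungal), erythromycin and ciprofloxacin (antibiotics) and aprepitant (antiemetic). This shows that the situation is plausible. It does not measure how often it would arise.

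**The case against.** The best case for the plan is that this is loose drafting and not a contradiction. One dose, 140 mg, complies with both sections. Section 15.16 reads as generic drug information: it refers to the study protocol from inside that protocol, and it carries a chronic graft-versus-host rule for patients not studied here. It defers to study-specific rules three times, and in the other two places it prints no dose at all. On that pattern 9.5 is the operative rule. Exclusion 3.29b also points to 9.5(a) for CYP3A modulators, so the protocol does identify where the rule sits. Section 8.0 is about adverse events, so the absence of an interaction rule there is unsurprising. Section 15.19 uses 15.16 as a list of agents to avoid and instructs no one to give 280 mg.

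Most of this is fair. A careful reader can reach 140 mg, and 15.19 is not itself a dosing instruction. But the comparison within 15.16 cuts the other way too. Where that section means to hand over entirely, it prints no number; for moderate inhibitors it prints one, and the sentence reads as complete. The pointer in 3.29b is in the eligibility criteria, which is not where someone managing a drug interaction during treatment would look. Nor is 9.5 plainly the section tailored to this trial, since it carries a rule for an 840 mg dose that is not used here. Someone who stops at 280 mg has complied with 15.16 as worded.

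The objection is also right that printing 140 mg everywhere would entrench an error if current guidance is 280 mg. Section 9.5 itself refers readers to the current Investigator's Brochure, which is not among the documents. The fix therefore has to start with the sponsor confirming the dose.

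**Conclusion.** The concern holds. For a patient on 420 mg who must take any of the 13 moderate inhibitors named in 15.16, the protocol prints both 140 mg and 280 mg, and the clause that might settle it neither ranks them nor says where the governing rule is. The discrepancy is twofold in nominal dose, or 140 mg a day, for the duration of inhibitor use.

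The conclusion rests on the wording of the two sections and assumes a patient at 420 mg. Section 15.16 is silent on patients already reduced to 280 mg or 140 mg, and nothing is concluded about them. The documents give no frequency of inhibitor use and no fold-change in exposure. No effect is claimed on exposure, toxicity rates, the MRD endpoint, the sample size or the analysis. It should be fixed because it is a conflicting dose instruction that bears on patient safety.

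**What to change.** Have the sponsor confirm the intended dose against its current guidance, then state it in one place.

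- If 140 mg is confirmed, replace the 280 mg sentence in 15.16 with: *For moderate CYP3A inhibitors, follow section 9.5 (140 mg for the duration of inhibitor use).* In 15.19, cite sections 9.5 and 15.16 together.
- If 280 mg is confirmed, change the figure in 9.5 to match, and state the dose for patients already at 280 mg or 140 mg.

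Three optional tidy-ups fit the same amendment: delete the 840 mg text in 9.5, delete the graft-versus-host sentence in 15.16, and give voriconazole one class (9.5 lists it as moderate, while 15.16 groups it with the strong inhibitors).

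The cost is negligible: one sentence and one cross-reference in the first case; one figure and a short dosing statement in the second. Design, sample size and analysis are untouched.
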